Date: April 9, 2019

Title: Importance of Sock Type in the Development of Foot Lesions on Low-difficulty, Short Hikes.

Description of document: Materials and Methods (Study Protocol: description of the clinical study, including objective and design. Statistical Analysis Plan (description of the statistical considerations for analyzing the data collected in the study.) results of the study (Results obtained in the study) and Supplementary data (protocol of measures and other tables).

Materials and Methods

1. Permission and participants

All participants signed an informed consent form, and permission for the study was obtained from the Bioethics Committee (reference 126/2016). The admission criteria were: be of legal age, have no current health problems that would hinder or prevent participation in the hike, and carry a backpack weighing less than 3 kg. Participants were asked to use specific hiking footwear (light, flexible, soft-soled, with good grip and breathable material) (low top hiking shoes), based on earlier studies [38-40]. They were also asked to do the entire hike following the instructions of an experienced guide and to not remove their footwear or socks before examination by a podiatrist.

2. Sock type and interventions performed

Socks were of two types: technical socks, designed for high performance sports use (Lurbel brand, models Tierra and Set), and non-technical socks for everyday use. The socks had different composition: Tierra (50% regeneractiv, 25% cool-teak, 17% polyamide ions, 8% lycra); Set (75% cotton, 17% polyamide, 8% lycra) and cotton (98% cotton, 2% elastane). The technical socks had reinforced weave in the toe, metatarsal and heel areas.

Participants were examined by trained podiatrists on three occasions to measure the study variables: at the start of the walk (km 0), at the end of the asphalt section (half way; km 14.5) and at the end (km 29.6). The protocol of measures was followed (supplementary data).

3. Study design, route description and participants

Weight (kg)

A clinical trial randomized, double blinded was designed to analyze the influence of different types of socks (technical and non-technical) on the appearance of foot injuries after a low-difficulty, short-term sport activity. The study follow the CONSORT criteria.

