To carry out the study, the hiker was previously registered. The researchers contacted the participants to explain the study. In addition, data on age, sex, foot number and associated diseases that prevented the completion of the route were obtained. One hour before starting the route, researchers who did not intervene in the exploration process, made registration and delivery to each hiker of two technical socks (1 Set and 1 Tierra) appropriate to the size of the foot and randomly for the right foot (RF) and left foot (LF). Likewise, it proceeded for non-technical socks (cotton), but in this case both feet wore the same type of sock. All the participants before the initial exploration had their socks put on for half an hour. The hike was low-difficulty, over a short distance [37]. The first 14.5 km were on asphalt and the last 15.1 km on dirt. The height range was 189 m and the pace was moderate, at 5 km/hour. The sample comprised 109 participants (53 men and 56 women). Two women had to give up the hike for personal reasons. Both wore technical socks.

The Table 1 explain the anthropometric characteristics of the participants and the distribution of the socks, differentiating by sex and feet.

Anthropometric variable	Total	Male	Female	
Gender		48.6%	51.4%	
Age (years)	44± 25	49± 21	36 ± 24	
Height (meters)	1.7± 0.1	1.7± 0.1	1.6± 0.1	

81.0±13.5

61.4±7.8

68.8±19.4

Table 1. Anthropometric variables, total sock distribution and sock distribution by gender.

BM	II	24.9± 3.6	26.6± 3.7	23.5± 9.1
Sock type di	istribution	Total %	Male %	Female %
LF sock	Tierra	40.4 (n=44)	35.8 (n=19)	44.6 (n=25)
	Set	29.4 (n=32)	35.8 (n=19)	23.3 (n=13)
	Cotton	30.2 (n=33)	28.4 (n=15)	32.1 (n=18)
RF sock	Tierra	29.4 (n=32)	35.8 (n=19)	23.3 (n=13)
	Set	40.4 (n=44)	35.8 (n=19)	44.6 (n=25)
	Cotton	30.2 (n=33)	28.4 (n=15)	32.1 (n=18)

Km=Kilometres, n=sample size, %=Percentage, ±=Standard deviation, kg=Kilogrammes, BMI=Body mass index, LF=Left foot, RF=Right foot.

4. Study variables

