The qualitative variables analysed were: gender, body mass index (BMI) by rank, sock type, dermal lesions (all lesions developed during the hike, both keratopathies with keratinisation disorder and dermatopathies without keratinisation disorder), muscle lesions (all lesions developed during the hike) and nail lesions (all nail lesions developed during the hike, both traumatic and non-traumatic onychopathies). The height and weight data obtained were used to calculate BMI by rank, interpreted according to the World Health Organization classification [41] (Table 2).

Table 2. Qualitative variables and categories. BMI= Body mass index.

Qualitative variable	Category	
Gender	Male Female	
BMI	Underweight (<18.5) Normal weight (18.5-24.99) Overweight (25.0-29.9) Obese ((>30)
Sock type	Technical (Tierra) Technical (Set) Non-technical (Cotton)	
Skin lesion	Blister Injury (Erosion & chafing) Reddened skin Urticaria Crevice H	Ieloma
Muscle lesion	Pain due inadequate warm Inflammation Muscle discomfort Sprain	
Nail lesion	Onychocryptosis Subungueal hematoma	

The quantitative variables analysed were: age, body mass index (BMI), temperature of each foot measured in two aspects (plantar and dorsal), and perimeter of each foot, measured in four areas (dorsal aspect of toes, instep, heel, tibia).

5. Measuring instruments

The height range and the pace hikers was controlled with a Garmin ETREX 20X GPS (Global Positioning System). Perimeter was measured with a flexible, non-elastic tape measure (Lawton 18-0160, precision 1 mm). Weight was measured using scales (Tanita UM-076, precision 0.1kg) and height was measured using the weight rod of different scales (SECA 704, precision 1 mm).

Temperatures were taken with an infrared thermometer (FTN Medisana, precision 0.18° C), calculating the mean of the three measurements. An intra rate of the measure was done to detect the error of the measure of the temperature, obtaining an error of 0.1452.

6. Statistical tests

The data were analysed using IBM SPSS Statistics for Windows, Version 22.0 (IBM, Armonk, New York). The statistical treatment consisted of data study and cleansing, descriptive variable analysis, normality test (Shapiro-Wilks test). The studies of normality were no significant (p-values between 0.000 y 0.044).

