Quantitative variables depending on whether the samples were paired or independent, Friedman's test for related samples and Kruskal-Wallis was performed for independent samples, both with Bonferroni correction for multiple testing was applied. For the qualitative variables the

chi-square or Fisher's exact test with a significance level of α = 0.05 was carried out. The variables analysed by logistic regression were quantified using the ODDS Ratio (OR). The effect size for the different variables was also calculated. First, for Kruskall-Wallis tests, the variation was between 0.443 y 0.888, and for Friedman tests, the variation was between 0.336 y 0.623. Therefore, in both cases the effect size could be considered median and high.

All p-values = 0.000 are less than 1 per 1000.

Results

After completing the first part of the hike, the most frequent dermal lesions among participants were blisters and erosions.

Table 3. Prevalence of skin, muscle and nail lesions during the 0-14.5 km of the hike by sex.

(0.14 = 1)				Fen	nale					Ma	ıle		
(0-14.5 km)		Tier	ra %	Se	et %	Cott	on %	Tier	ra %	Set	%	Cott	on %
Skin lesion	%Tt.	RF	LF	RF	LF	RF	LF	RF	LF	RF	LF	RF	LF
Blister	12.8	0.0	4.0	8.0	7.7	22.2	27.8	0.0	5.3	5.3	0.0	6.7	13.3
Erosion	2.8	0.0	0.0	0.0	0.0	11.1	5.6	0.0	0.0	0.0	0.0	6.7	0.0
(0.44.5.1)				Fer	male					Ma	ıle		
(0-14.5 km)		Tier	ra %	Se	et %	Cott	on %	Tier	ra %	Set	%	Cott	on %
Muscle lesion	%Tt.	RF	LF	RF	LF	RF	LF	RF	LF	RF	LF	RF	LF
Pain due inadequate warm	21.1	23.1	27.8	8.0	7.7	27.8	27.8	10.5	15.8	10.5	0.0	13.3	13.3
Inflammation	2.8	0.0	4.2	4.0	0.0	0.0	0.0	0.0	10.5	10.5	0.0	0.0	0.0
Muscle discomfort	1.8	0.0	0.0	0.0	0.00	0.0	0.0	5.3	5.3	0.0	0.0	0.0	0.0

Km=Kilometres, %=Percentage, Tt=Total, RF=Right foot, LF=Left foot.

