The study of the perimeter of hikers' feet analysed in total and by gender, in relation to distance and sock type, did not reveal significant results (data not shown).

Table 7. Probability of suffering skin and muscle lesions in relation to anthropometric variables and sock type throughout the hike.

1	PROBABILITY SKI	N LESIONS	PROBABILITY M	USCLE LESIONS		
Dist	ance:	Distance: 14.5-29.6 Km	Distance: 0-14.5 Km			
96% If	female	90% If male	100% I	f male		
100% If non-	technical sock	100% If non-technical sock	67% If non-te	chnical sock		
Direct relation	Inverse relation	Inverse relation	Direct relation	Inverse relation		
BMI	Age	Age	BMI	Age		

km=Kilometre, %= Percentages, BMI=Body mass index.

It was possible to study the relation between variables and predict the probability of lesions developing during the hike using logistic regression analysis (Table 7). Women have a higher probability than men of suffering skin lesions in hikes of up to 14.5 km. However, men have a higher probability than women of suffering skin lesions on hikes of 14.5 to 29.6 km and muscle lesions on hikes of up to 14.5 km.

The non-technical socks showed the highest probability of wearers suffering dermal and muscle lesions, both from 0-14.5 km and from 14.5 km to the end of the hike. The probability of dermal and muscle lesions developing in relation to the quantitative variables showed direct and inverse relations. From 0-14.5 km, the BMI and age of hikers are directly and inversely related, respectively, both in dermal and in muscle lesions. In the second part of the hike, age continued to show an inverse relation with skin lesions, but no relation with BMI was identified (Table 7).

Supplementary data

Protocol of Measures. Top shows the protocol of measure at the starting point (0 km). Middle part includes the protocol of the first part of the hike (0-14.5 km) and lower part of the table reflex the measurement protocol of the second part of the hike (14.5-29.6 km)

PPOTOCOI	OF MEASURES
STARTING POINT (0 Km)	OF MEASURES
Dorsal Number: Gender: Gender:	Foot size Weight Size
Body mass index (BMI):	The state of the s
	Previous Alterations on skin, muscles or
nails	
	rature LF
Plantar Plantar	
Dorsal Dorsal	
Perimeters RF: (Three different measures)	Perimeters LF: (Three different measures)
tibia	tibia
hell	hell
toes instep	toes instep
FIRST PART OF THE HIKE (0-14.5 Km)	Perimeters RF: (Three different measures)
	tibia
Temperature RF: (Three different measures)	
Plantar	

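### No described test uses the km-0 perimeter to compare change between sock types, and the bare non-significant result for perimeter gives no estimate, so it is not evidence of no sock effect.

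*Combined protocol and SAP*

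**What the plan says.** Section 4 (Study variables) lists among the quantitative variables the "perimeter of each foot, measured in four areas (dorsal aspect of toes, instep, heel, tibia"). Section 2 places the examinations "at the start of the walk (km 0), at the end of the asphalt section" and at the finish. The Protocol of Measures in the Supplementary data has perimeter fields for both feet at the starting point, for example "Perimeters RF: (Three different measures"), and again at both later points.

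Section 6 (Statistical tests) gives the methods for quantitative variables: "Friedman's test for related samples and Kruskal-Wallis was performed for independent samples, both with Bonferroni correction for multiple testing was applied". It describes no change score, baseline covariate or sock-by-distance test. The 0.05 level is written only for the qualitative variables: "chi-square or Fisher's exact test with a significance level of α = 0.05 was carried out".

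Section 3 says that cotton wearers had cotton on both feet, while technical-sock wearers had Set on one foot and Tierra on the other. Cotton versus technical is therefore a comparison between different hikers.

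The Results give perimeter one sentence, covering the total sample and each gender: it "in relation to distance and sock type, did not reveal significant results (data not shown").

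**The concern.** If a sock affects swelling during the hike, the effect shows as a different change in perimeter from km 0. The described tests approach this from two sides and do not join them.

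- Kruskal-Wallis at a given distance compares the perimeters of different people, so stable differences in foot size enter as noise.
- Friedman within one sock type removes foot size, but it only asks whether perimeter changed in that sock. A significant result in one sock and not in another is not a test of the difference, and two non-significant results do not bound it.

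The layout is visible for temperature. Tables 5, 6, A and B give p-values between socks at each distance and p-values between distances within each sock, and none for the difference in change. For perimeter the same layout is an inference, because no data are shown.

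At stake is how the sentence is used. Without an estimate, interval or margin, a reader cannot tell a well-bounded null from an uninformative one.

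**Working it through.** The document states no power, target difference, SD or correlation for perimeter, so there is no figure of its own to reproduce.

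**Inputs from the document.** "The sample comprised 109 participants (53 men and 56 women"). Table 1 gives 33 in cotton, hence 109 − 33 = 76 in technical socks. By sex this is 38 vs 18 (women) and 38 vs 15 (men).

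**Assumptions.** Normal data; two-sided 0.05 without correction; a sock difference d of 0.5 or 0.3 between-hiker SD; correlation r between the km-0 and later perimeter of the same foot of 0.5, 0.8 or 0.9.

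**Formulas.** Noncentrality = (d / k) × √(n1·n2/(n1+n2)), with k = 1 for raw values, √(2(1−r)) for change from km 0, and √(1−r²) for ANCOVA. Here √(76×33/109) = 4.80.

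- Raw, d = 0.5: 0.5 × 4.80 = 2.40; t-test power 66%, and 63% for the rank test by simulation.
- ANCOVA, d = 0.5, r = 0.5: k = 0.866; 2.40/0.866 = 2.77; power 78%.
- ANCOVA, d = 0.5, r = 0.8: k = 0.6; 2.40/0.6 = 4.00; power 98%.
- Change score, d = 0.5, r = 0.5: k = √(2×0.5) = 1, so no gain over raw values.

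**Simulated power** (4,000 runs, 76 vs 33). The Friedman column is the cotton group alone, with the whole change in cotton, present at 14.5 km and persisting.

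| d (SD) | r | Raw rank test | Rank test on change | ANCOVA on km 0 | Friedman, cotton only |
|---|---|---|---|---|---|
| 0.5 | 0.5 | 63% | 63% | about 77% | 67% |
| 0.5 | 0.8 | 63% | 95% | about 97% | 98% |
| 0.5 | 0.9 | 63% | >99% | >99% | >99% |
| 0.3 | 0.5 | 28% | 28% | 38% | 29% |
| 0.3 | 0.8 | 28% | 59% | 65% | 64% |
| 0.3 | 0.9 | 28% | 87% | 90% | 91% |

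**By sex.** For d = 0.5 the raw rank test has about 39% power in women and 34% in men; for d = 0.3, about 17% in each.

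**With Bonferroni.** At 0.05/3 (three sock pairs, an assumption), the raw figures for d = 0.5 fall to about 47% overall, 23% in women and 19% in men.

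**Sensitivity to group sizes.** The Results percentages at 29.6 km fit 16/76 = 21.1% and 17/31 = 54.8%, whereas section 3 says both dropouts wore technical socks. These passages need reconciling, but with 76 vs 31 the raw t-test power for d = 0.5 is 64% instead of 66%.

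**The case against.** A reader might infer that km 0 was ignored and that a real sock effect on swelling would often have been missed. The document does not support that. Its perimeter sentence covers distance as well as sock type, and Friedman across the three distances uses km 0 and removes foot size. If swelling differs between socks, perimeter must change in at least one of them. The last two columns of the table show that, when the whole change is in cotton and r is 0.8 or 0.9, Friedman in cotton alone has about the same power as ANCOVA. The high correlations that favour baseline adjustment favour the existing distance test too. The raw power figures therefore describe one of the two tests, not the analysis as a whole.

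Three further objections have weight. A raw comparison reflects mostly foot size only if r is high: the share of variance explained by km 0 is r², 81% at r = 0.9 but 25% at r = 0.5. The analysis by gender removes sex as a source of noise within those strata. And the document reports non-significance without claiming that socks have no effect on perimeter; its stated objective is foot injuries.

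The objection does not supply the missing comparison. Friedman cannot say whether the change differs between socks, and non-significant results without numbers set no limit in mm on a difference.

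It is also fair that km 0 is not a pre-sock baseline. Socks had been worn for half an hour, and km-0 temperatures already differ widely by sock (Table A, dorsal right foot: 35.0 vs 20.7 °C). This narrows the question to change during the hike; it does not defeat the adjustment.

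**Conclusion.** The point holds in limited form. No described test compares the change in perimeter between sock types, although the km-0 value needed for it is on the form, and the reported sentence cannot serve as evidence of no sock effect. The between-sock test alone has about 63% power for 0.5 SD and 28% for 0.3 SD, given the Table 1 group sizes and no correction. How much adjustment gains is uncertain: at 0.5 SD, ANCOVA gives about 77% at r = 0.5 and 97% at r = 0.8. The SD, correlation and effect size are all assumed. That perimeter was compared unadjusted is inferred from section 6 and the temperature tables. Low-to-moderate severity: perimeter is one listed variable, and the main conclusions rest on lesions.

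**What to change.** For each perimeter site, estimate the sock difference at 14.5 and 29.6 km by ANCOVA with the same foot's km-0 perimeter as covariate, or by a mixed model with a sock-by-distance term and a hiker random effect. Prefer either to a simple change score, which gains nothing at r = 0.5.

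- Technical vs cotton: use the hiker as the unit, for example the mean of both feet.
- Tierra vs Set: compare within hiker, since each technical-sock wearer had one of each. Averaging the feet cannot answer this.
- Report each difference in mm with a 95% CI in place of the bare non-significance statement. Claim no relevant effect only if the interval excludes a margin stated in mm.
- State that km 0 followed half an hour in the socks, so the estimate covers change during the hike only.

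The cost is a re-analysis of recorded data and one small table. The downside is that any sock effect arising before km 0 is adjusted away.

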None of the other dermal lesions included in the evaluation (reddened skin, urticaria, crevice and heloma) were detected. Significant differences were found between the percentage of dermal lesions in hikers wearing technical socks (6.6%) and non-technical socks (36.4%) (p-value=0.000). The women had a higher percentage of dermal lesions (23.2%) than the men (7.5%) (p-value=0.034), regardless of sock type. Moreover, the percentage of women with dermal lesions was significantly higher among wearers of non-technical socks (50%) than in wearers of technical socks (10.5% had lesion) (p-value=0.002). Particularly the women presented more blisters in both RF and LF when they wore cotton sock compared to the Tierra and Set socks (RF p-value = 0.050, LF p-value = 0.042). In the case of men, there was no difference in any of the skin lesions at 14.5 km on any foot compared to the sock used (Table 3). The most frequent muscle lesions at the end of the first part of the hike were pain due inadequate warm (21.1%), inflammation (2.8%) and muscle discomfort (1.8%). No sprains or nail disorders were detected at the end of the first part of the hike. No difference between any of muscle lesions analyzed and technical and non-technical socks were found. By sex, no differences were found regarding technical and non-technical socks or concerning the model used sock on each foot (Table 3).

Table 4. Prevalence of skin, muscle and nail lesions during the 14.5-29.6 km of the hike by sex.

(14.5-29.6 km)				Fema	ale					N	I ale		
(14.5-29.6 KM)		Tie	rra %	Set	%	Cott	on %	Tier	ra %	Se	et %	Cott	on %
Skin lesion	%Tt.	RF	LF	RF	LF	RF	LF	RF	LF	RF	LF	RF	LF
Blister	19.6	7.7	12.0	20.0	7.7	25.0	12.5	5.3	0.0	5.3	21.1	6.7	0.0
Erosion	7.5	0.0	4.0	8.0	0.0	12.5	18.8	0.0	0.0	0.0	0.0	20.0	13.3
Reddened skin	3.7	0.0	0.0	0.0	0.0	18.8	18.8	0.0	0.0	0.0	0.0	6.7	6.7
Urticaria	0.9	0.0	0.0	0.0	0.0	6.3	6.3	0.0	0.0	0.0	0.0	0.0	0.0
Crevice	0.9	0.0	0.0	0.0	0.0	0.0	0.0	0.0	0.0	0.0	0.0	6.7	0.0
Heloma	0.9	0.0	0.0	0.0	0.0	0.0	0.0	0.0	0.0	0.0	0.0	6.7	6.7
(14.5-29.6 km)			Female			Male							

		Tier	ra %	Set	t %	Cott	on %	Tier	a %	Se	et %	Cott	on %
Muscle lesion	%Tt.	RF	LF	RF	LF	RF	LF	RF	LF	RF	LF	RF	LF
Pain due inadequate warm	11.2	15.4	4.0	4.0	7.7	0.0	12.5	10.5	0.0	5.3	10.5	0.0	0.0
Inflammation	0.9	0.0	4.0	4.0	0.0	0.0	0.0	0.0	0.0	0.0	0.0	0.0	0.0
Muscle discomfort	0.9	0.0	0.0	0.0	0.0	0.0	0.0	0.0	0.0	5.3	0.0	0.0	0.0
Sprain	0.9	0.0	0.0	4.0	0.0	0.0	0.0	0.0	0.0	0.0	0.0	0.0	0.0
(14.5-29.6 km)				Fem	ale					N	Iale		

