(14.5-29.0 KIII)		Tier	ra %	Set	t %	Cott	on %	Tierr	a %	Se	et %	Cott	on %
Nail lesion	%Tt.	RF	LF	RF	LF	RF	LF	RF	LF	RF	LF	RF	LF
Onychocryptosis	0.9	7.7	0.0	0.0	0.0	0.0	0.0	0.0	0.0	0.0	0.0	0.0	0.0
Subungual hematoma	1.9	0.0	0.0	0.0	0.0	6.3	6.3	0.0	0.0	0.0	0.0	6.7	6.7

Km=Kilometres, %=Percentage, Tt=Total, RF=Right foot, LF=Left foot.

In the second part of the hike, a greater variety of dermal lesions was detected. The most prevalent were blisters, erosions and reddened skin. Again, no urticaria, reddened skin, crevices, or helomas were detected with either technical sock. Differences were found between the percentage of dermal lesions among hikers wearing technical socks (21.1%) or non-technical socks (54.8%) (p-value=0.001). By gender, the percentage of women and men with dermal lesions was higher among wears of non-technical socks (women 68.8% and men 40%) than among wearers of technical socks (women 26.3% and men 15.8%) but the differences only were significant in women (p-value=0.006). Considering the sock used in each foot, in the case of women, presented more reddened skin in both RF and LF if they used cotton sock compared to the Tierra and Set (RF and LF p-values=0.023). In the case of men, they presented more blisters in the LF if they used Set sock than cotton or Tierra (p-value=0.021) and more erosion in the RF if they used cotton sock in comparison with the Tierra or Set (p-value=0.018) (Table 4). A greater variety of total muscle lesions was also detected in the second part of the hike: pain due to inadequate warm, inflammation, muscle discomfort and sprain. No differences were found between any of the muscular injuries analysed and the technical and non-technical socks neither by sex (Table 4).

Nail lesions like onychocryptosis (0.9%) and subungual hematomas (1.9%) were infrequently and developed only in the second part of the hike. No difference between any of the nail lesions analyzed and technical and non-technical socks were found. By sex, no differences were found (Table 4).

The temperature comparisons between technical and non-technical socks, regardless of distance, foot, measurement area and sex, showed significant differences. The Friedman test was performed (p value <0.005) for the comparisons between paired samples and the Kruskal-Wallis test was performed (p value <0.009) for independent samples. (Supplementary data, tables A, B).

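### Table 7 reports logistic-regression probabilities of 67–100% that cannot be the lesion risks of the groups named, gives no odds ratio, and leaves two second-half statements without a supporting estimate

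*Combined protocol and SAP*

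**What the plan says.** Section 6 (Statistical tests) states that variables in the logistic regression are expressed as odds ratios. The Results contain no odds ratio, confidence interval, coefficient, covariate list or reference category.

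Table 7 instead gives percentages described as probabilities of lesions:

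- Skin, first part: 96% if female; "100% If non- technical sock". This column's distance is lost in the extracted text; it is read as 0–14.5 km from the paragraphs below the table.
- Skin, 14.5–29.6 km: 90% if male, 100% if non-technical sock.
- Muscle, 0–14.5 km: 100% if male, 67% if non-technical sock.

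The text below Table 7 says: "However, men have a higher probability than women of suffering skin lesions on hikes of 14.5 to 29.6 km and muscle lesions". The sentence goes on to limit the muscle part to the first 14.5 km. The next paragraph says: "The non-technical socks showed the highest probability of wearers suffering dermal and muscle lesions, both from 0-14.5 km and from 14.5 km" to the finish.

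The descriptive results read differently. For the first half: "The women had a higher percentage of dermal lesions (23.2%) than the men (7.5" per cent). For second-half skin lesions, rates were higher in "non-technical socks (women 68.8% and men 40%) than among wearers of technical socks (women 26.3% and men 15.8" per cent). For second-half muscle lesions: "No differences were found between any of the muscular injuries analysed and the technical and non-technical socks neither by sex".

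**The concern.** A percentage labelled as a probability if female, or if wearing a non-technical sock, will be read as the risk in that group. On that reading Table 7 contradicts the lesion frequencies reported a few paragraphs earlier. Two statements drawn from the regression also lack support: that men have the higher second-half skin risk, and that non-technical socks carry the highest second-half muscle risk.

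A reader would conclude that skin lesions are nearly certain in cotton socks, that men are at greater skin risk late in the hike, and that technical socks protect against muscle lesions in the second half. The reported data support none of these.

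**Working it through.** **Recovering the counts.** Group sizes come from Section 3 and Table 1: 53 men and 56 women; 33 in cotton (15 men, 18 women); 76 in technical socks (38 men, 38 women). The percentages are those in the Results text.

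- First half: women 9/18 + 4/38 = 13/56 = 23.2%; men 4/53 = 7.5%; cotton 12/33 = 36.4%; technical 5/76 = 6.6%.
- Second half: cotton women 11/16 = 68.8%, cotton men 6/15 = 40%, technical women 10/38 = 26.3%, technical men 6/38 = 15.8%. Hence women 21/54 = 38.9%, men 12/53 = 22.6%, cotton 17/31 = 54.8%, technical 16/76 = 21.1%.

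Fisher's exact test on these counts reproduces the document's p-values:

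| Comparison | Recomputed | Stated |
|---|---|---|
| First half, sex | 0.0337 | 0.034 |
| First half, sock | 0.0002 | 0.000 |
| First half, sock, women | 0.0021 | 0.002 |
| Second half, sock | 0.0011 | 0.001 |
| Second half, sock, women | 0.0057 | 0.006 |

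**Table 7 against the observed risks.**

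| Outcome | Group | Table 7 | Observed |
|---|---|---|---|
| Skin, first half | Women | 96% | 13/56 = 23.2% |
| Skin, first half | Non-technical | 100% | 12/33 = 36.4% |
| Skin, second half | Men | 90% | 12/53 = 22.6% |
| Skin, second half | Non-technical | 100% | 17/31 = 54.8% |
| Muscle, first half | Men | 100% | at most 17/53 = 32.1% |
| Muscle, first half | Non-technical | 67% | at most 14/33 = 42.4% |

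The muscle bounds add up Table 3 cells as if no hiker appeared in two of them. Men: pain 2+3+2+0+2+2 = 11, inflammation 2+2 = 4, discomfort 1+1 = 2, total 17. Cotton: pain 5+5+2+2 = 14, with every other muscle cell zero. As a check, the whole-sample figures of 21.1%, 2.8% and 1.8% are 23, 3 and 2 of 109, so at most 28 hikers of either sex had one of these lesions. All 53 men cannot have had one.

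Covariate adjustment does not close the gap. In a maximum-likelihood logistic model with an intercept and a group indicator, the mean fitted probability in that group equals its observed proportion, whatever else is in the model. In a model with sex and sock only, the largest fitted probability is 50% in the first half and 65% in the second.

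**Second-half skin lesions by sex.** Women are higher in both sock groups: 68.8% versus 40%, and 26.3% versus 15.8%. Crude comparison: 21/54 versus 12/53, Fisher p = 0.094. With sex and sock in the model, the odds ratio for women versus men is 2.35 (95% CI 0.95–5.79, p = 0.064).

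This uses 16 cotton and 38 technical women, the only split that fits the percentages. Section 3 says of the withdrawals: "Two women had to give up the hike for personal reasons. Both wore technical socks", which implies 18 and 36. The percentages are then not whole counts. The nearest integers, 12–13 of 18 and 9–10 of 36, give odds ratios of 2.20 to 2.63 with lower limits of 0.89 to 1.07. The direction is the same.

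**Second-half muscle lesions by sock.** Table 7, as extracted, has no second-half muscle column. From Table 4, pain occurred in 11.2% = 12/107 hikers. The cotton cells give 2/31 (12.5% of 16 women, left foot; all other cotton pain cells zero), leaving 10/76 in technical socks. Fisher p = 0.50. The crude direction is opposite to the text, but the counts are too few to show either direction.

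**The case against.** Four points can be made for the document.

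1. **The percentages may be predictions for one profile.** The text speaks of prediction, and a model with age and BMI could return 67–100% for some hiker. That is possible, but no profile is stated and the labels name only sex or sock. On this reading the entries are uninterpretable.

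2. **Age adjustment favours the authors on sex.** Table 1 gives ages of 49 for men and 36 for women, and an inverse age relation is reported for second-half skin lesions. Adjusting for age would therefore move the estimate towards the document's statement. If those ages are means, an age odds ratio of exp(−10 × ln 2.35 / 13) = 0.52 per decade would cancel the 2.35. This is only illustrative: Table 1 does not call the ages means, and their weighted average, (53 × 49 + 56 × 36)/109 = 42.3, differs from the stated 44. The interval for 2.35 also includes 1. The statement is therefore unsupported as reported; it has not been shown to be false.

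3. **A non-significant test for each muscle lesion does not contradict a higher modelled risk.** This is correct in principle. It still leaves the second-half muscle statement with no estimate behind it.

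4. **The recording form has a field for other lesions, so the muscle bounds may be incomplete.** The bounds cover the lesion types that Table 2 lists, and the text says no sprains occurred in the first half. Untabulated lesions would have to be very numerous to bring the men to 100%.

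It is also fair that sock type, the trial's stated objective, is addressed by the direct skin comparisons, which stand.

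**Conclusion.** The concern holds. Table 7's percentages exceed the observed skin risks by about 45 to 73 percentage points (100 − 54.8 = 45.2; 96 − 23.2 = 72.8). They exceed the upper bounds for muscle by about 68 points in men (100 − 32.1) and 25 points in cotton wearers (67 − 42.4). They cannot be the risks of the groups named, and without a stated covariate profile they have no other usable meaning. The measure named in Section 6 is absent.

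The second-half sex statement is unsupported: the unadjusted and sock-stratified rates point the other way, and no age-adjusted estimate is given. The second-half muscle statement has no estimate behind it, and the Table 4 pain counts do not support it.

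The conclusion rests on counts recovered from rounded percentages, which reproduce the five stated p-values, and, for muscle, on the tabulated lesion types being complete. No view is taken on the direction of the sex difference in first-half muscle lesions, because one female cell in Table 3 (27.8% where n = 25) is not a possible fraction. This must be corrected before the regression results are used.

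**What to change.** - Refit the logistic models and state the covariates, the reference categories and how the events are counted. Check the coding of sex.
- Replace the Table 7 percentages with adjusted odds ratios and 95% confidence intervals for sock, sex, age and BMI. If probabilities are wanted, give model-standardised risks with intervals and say to whom they apply.
- Check how the percentages were produced. As conjecture only: one minus the Fisher p-value for the four skin comparisons is 96.6%, 99.98%, 90.6% and 99.9%, close to the four skin entries.
- Withdraw the second-half sex statement unless an adjusted odds ratio with its interval supports it. Withdraw the second-half muscle statement about non-technical socks.
- Reconcile the women's second-half denominators (16 cotton and 38 technical from the percentages) with Section 3's account of the two withdrawals.

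The cost is one table re-run and relabelled, with no new data. The effects will look less dramatic, and with 33 second-half skin events (21 + 12) the adjusted sex odds ratio will have a wide interval.
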